#### **GMFCS** level

A frequency table for GMFCS level at baseline (V2) for CP subjects will be displayed for SES and FAS of MP and SES of OLEX.

#### **Protocol deviations**

Protocol deviations will be classified into minor and major violations during the BDRM. Major protocol deviations (deviations leading to exclusion from per protocol set) will be summarized for all randomized/ assigned subjects of the MP and all subjects that entered the OLEX using a frequency table.

All protocol deviations will be listed, including their classification.

#### Diseases specific and general medical history and concomitant diseases

Medical history and concomitant diseases will be coded according to the MedDRA and displayed with respect to System Organ Class and preferred terms for SES of MP and FAS. Concomitant diseases will also be tabulated for the SES of OLEX; medical history will be tabulated for the MP only. A detailed description of the rules to be used to classify medical history and concomitant diseases can be found in Appendix 1.

The following data on the medical history of sialorrhea will be analyzed descriptively for MP (SES and FAS) and for OLEX (SES):

- Primary reason (frequency table).
- Duration since first diagnosis of sialorrhea in months: (date of baseline injection visit in the main period date of start of sialorrhea + 1)/30.5 (summary statistics).
- Intellectual disability (frequency table).

In case of missing days (but month given) for the start of sialorrhea, the date will be set to the first day of the respective month. In case the month is also missing, no imputation will be done and the duration will be left as missing.

#### Previous and concomitant therapies

Previous therapies are defined as therapies for which the stop date is before the date of the first injection of NT 201 or Placebo.

For concomitant therapies of MP (and not OLEX) the following conditions have to be fulfilled:

- stop date is at or after start of first injection of MP.
- start date is not after start of treatment of the OLEX.
- not ongoing at the end of MP.

For concomitant therapies of MP and OLEX the following conditions have to be fulfilled:

- stop date is at or after start of first injection of OLEX or ongoing at MP/ OLEX.
- start date is not after start of treatment of the OLEX.

For concomitant therapies of OLEX (and not MP) the following conditions have to be fulfilled:

- stop date is at or after start of first injection of OLEX or ongoing at OLEX.
- start date is after start of treatment of the OLEX.

A detailed description of the rules to be used to classify previous therapies and concomitant therapies can be found in Appendix 1. Classes of non-drug treatments are derived from the observed data before database close in order to display frequencies of non-drug treatments. Indications for previous and concomitant therapies will not be coded and will only be listed.

Frequencies of previous and concomitant treatments will be given based on different Anatomical Therapeutic Chemical (ATC) code levels of the World Health Organization (WHO) (dictionary version in effect at database closure) as well as by generic names. Previous therapies will not be tabulated for the OLEX, only for the MP. Previous medication will be tabulated for SES of MP and FAS and previous non-drug treatment only for SES of CONFIDENTIAL Page 37 of 46

```
Template: tem-sap-v4.0-20151126
```

File name: MRZ60201\_3091\_1-sap-final v1.0-2019-06-21.docx

MP. Concomitant therapies for the MP will be analyzed for the SES of the MP and FAS. Concomitant therapies for the OLEX will be analyzed for SES of the OLEX.

#### **Duration of exposure**

The injection cycle length will be determined for each injection cycle. The injection visit will be regarded as start of a cycle and the day before the next injection (or the last available visit in case of a discontinued cycle or the last cycle) will be regarded as end of cycle. Furthermore, the period length for OLEX and the length of the entire study period will be analyzed.

The injection cycle length in weeks will be summarized descriptively for each cycle (SES of MP, FAS, SES of OLEX):

- Injection cycle length of 1st injection cycle in weeks: if 1st cycle is the last cycle: (date of last visit – date of 1st injection V2 + 1)/7 else: (date of 2nd injection – date of 1st injection V2)/7 (rounded to one decimal).
- Injection cycle length of2nd injection cycle in weeks: if 2nd cycle is the last cycle: (date of last visit – date of 2nd injection V6a + 1)/7 else: (date of 3rd injection – date of 2nd injection V6a)/7 (rounded to one decimal).
- Injection cycle length of3rd injection cycle in weeks: if 3rd cycle is the last cycle: (date of last visit – date of 3rd injection V10a + 1)/7 else: (date of 4th injection – date of 3rd injection V10a)/7 (rounded to one decimal).
- Injection cycle length of4th injection cycle in weeks: (date of last visit – date of 4th injection V14a + 1)/7 (rounded to one decimal).

In case a cycle is omitted, the day before date of next available injection will be used as end date for the calculation of the injection cycle length.

Furthermore, frequency tables for the injection cycle length will be displayed for SES of MP, FAS and SES of OLEX) (< 14 weeks, 14-18 weeks and >18 weeks).

The length of entire study period is defined as the sum of the duration of all injection cycles and will be summarized descriptively (SES of MP, FAS).

The period length of the OLEX period is defined as the sum of the duration of all injection cycles of the OLEX and will be summarized descriptively (SES of OLEX).

#### Extent of exposure

The extent of exposure will be determined for each injection cycle. For each subject and injection the total injected NT 201 units per injection (which will be zero for subjects treated with placebo) will be divided by the subject's body weight at the corresponding injection visit. This ratio will be classified into the following categories: 0 U/kg, ]0,1.5[ U/kg, [1.5, 1.8[ U/kg, [1.8, 2.2[ U/kg, [2.2, 2.5] U/kg and >2.5 U/kg.

A frequency table will display the number and percentage of subjects per (above given) categories of injected NT 201 units/{kg body weight at respective injection} per injection. Furthermore, the total injected NT201 units per injection will be analyzed for the following classes: <25 U, [15, 50[ U, [50,75[ U, 75 U, >75 U. Numbers will be based on the SES/ FAS of the MP for the first injection and on the SES of the OLEX for the injections within the OLEX.

OLEX tables for extent of exposure will only be presented irrespective of main period treatment.

Subjects with dose reduction or with differences in actual/ randomized treatment will be listed.

# Treatment compliance, method of administration of injection and use of analgesics and/or sedatives during injection

For the NT 201 group dosages will be given according to the predefined volumes of fixed total doses defined for each of the six body-weight classes (see Table 8 below).

[figure not shown]
In general for subjects with a body weight of 12-30 kg the total dose is approximately 2 U/kg. Subjects with a body weight  $\ge 30$  kg will receive a fixed total dose of 75 U. Due to the unitary concentration of the NT 201 solution the dose adjustment will be performed by adapting the injection volumes for each dose group (see Table 8).

Dosages will be adapted to actual body weight of subjects at each injection visit according to the dosage instructions. The subject's body weight will be re-determined at each injection visit, and if the body weight has increased (or decreased) over the limit of the class then the subject will be treated in the next higher (or lower) dosage group accordingly.

In the placebo group (only during MP), subjects will receive the respective volume of placebo solution (0.9% sodium chloride, sucrose and human serum albumin) as in the NT 201 treatment group according to their bodyweight classification.

 Table 8: Dosing scheme

CONFIDENTIAL Template: tem-sap-v4.0-20151126 File name: MRZ60201 3091 1-sap-final v1.0-2019-06-21.docx Page 39 of 46

The treatment compliance will be calculated for each cycle in percentage by (100 \* Total volume injected [mL]/Total volume planned [mL]). For MP the compliance will be displayed using descriptive summary statistics for SES of MP and FAS. For OLEX the total compliance (2nd, 3rd and 4th injection cycle together) and the compliance per injection cycle will be displayed using descriptive summary statistics for the SES of the OLEX. The total compliance is calculated as the mean compliance per subject for all performed injections of OLEX.

If a dose reduction is documented for a subject then the reduced planned dose will be used for calculation of the compliance in the next cycle. E.g. if a subject had an adverse event with action taken = 'dose reduced' in cycle 3 then it will be assumed that for the subject the reduced dose was documented in cycle 4. The dosing scheme with dose reduction is given in Table 9.

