#### Dose regimens for the extension period

There will be no placebo group in the extension period. The regimen for the administration of NT 201 will be the same body weight-adjusted dosing scheme as for the main period. Dosages will be adapted to actual body weight of subjects at each injection visit according to the dosage instructions.

The subject's body weight will be re-determined at each injection visit, and if the body weight has increased (or decreased) over the limit of the class then the subject will be treated in the next higher (or lower) dosage group accordingly. For details see Section 8.2.3.

No dose reduction due to AE is allowed for the second injection cycle (V6). If, in the opinion of the investigator, a dose reduction is advised, the dose can be reduced for the third injection cycle (V10) at the earliest. Only one dose reduction due to AE is allowed during the entire study period.

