## 8.2.3 Selection and timing of doses for each subject

For selection of doses, see Section 8.2.2; for timing of doses see Sections 6.1.2 and 9.2. No other dose levels and no other timing will be permitted.

The principle of by-weight dosing set out in Section 8.2.2 leads to the following table of doses for guidance of the investigator (Table 2).

Table 2 shows the amount of IP to be administered for each subject at each visit, according to the subject's body weight as determined at that visit.

Therefore:

- The subject's body weight will be determined immediately before each injection session, and if the body weight has increased (or decreased) then the subject will be treated in the next higher (or lower) dosage group.
- At each injection session (V2, V6, V10 and V14), a total of four injections will be administered, one in each gland (left and right parotid, left and right submandibular).

If a treatment-emergent adverse event occurs that the investigator considers as demanding a reduction in dose level, this reduction can only be implemented at the following injection visit of the extension period (V10 or V14) if the dose was not reduced because of weight loss at the same visit.

For reduced dose at the third and fourth administration of study medication (following a relevant adverse event; see Section 8.1.1.2 for details), each subject will be treated at the dose level set out in Table 2. For subjects in the smallest weight group (12 to 15 kg) dose reduction to a reduced level is not allowed; the only option is reduction to zero, i.e., discontinuation of the subject's participation in this study.

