### 10.1.3 Categories of actions taken and outcome

Action taken with the IP:

- Drug withdrawn (no further study injections given).
- Dose reduced (at the next injection possible i.e. at V10a [injection cycle 3] or V14a [injection cycle 4] only, due to weight loss or AEs).
- Dose increased (at next injection visit i.e. at V10a or V14a only, according to weight gain of subject).
- Dose not changed.
- Unknown.
- Not applicable.
- Drug withdrawn temporarily (further study injections delayed).

The reportable outcomes and/or sequelae of an AE are as follows:

- Recovered/resolved.
- Recovering/resolving.
- Not recovered / not resolved.
- Recovered / resolved with sequelae.
- Fatal.
- Unknown.

If there is more than one AE, only the AE leading to death will be attributed with a "fatal" outcome.

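### The SAP's extension-period compliance rule moves the planned dose one cycle after an AE, which mis-scores children whose reduction takes effect later or was due to weight loss

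*SAP*

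**What the plan says.** SAP 7.6 (Treatment compliance) computes compliance for each cycle as 100 times total volume injected over total volume planned. The planned volume normally follows the weight-class table (Table 8): "Dosages will be adapted to actual body weight of subjects at each injection visit according to the dosage instructions". Once a reduction is documented, "the reduced planned dose will be used for calculation of the compliance in the next cycle". The SAP's example takes the trigger from the AE record: "if a subject had an adverse event with action taken = 'dose reduced' in cycle 3", the reduced dose is assumed for cycle 4. The reduced scheme is Table 9, whose heading refers to the third or fourth injection. The text below it carries a cycle 3 reduction forward to cycle 4. Extension-period compliance is summarised per cycle and as a per-subject mean over the extension injections performed.

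The protocol sets timing and reason differently. Section 8.2.2 (Dose regimens for the extension period) rules out an AE reduction in the second cycle and says that "the dose can be reduced for the third injection cycle (V10) at the earliest". Section 10.1.3 defines the action *dose reduced* as taking effect at the next possible injection, namely "at V10a [injection cycle 3] or V14a [injection cycle 4] only, due to weight loss or AEs". Section 8.2.3 permits an AE reduction only "if the dose was not reduced because of weight loss at the same visit", and gives no reduced level for the 12 to 15 kg group.

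**The concern.** The SAP rule assumes that a reduction always takes effect one cycle after the AE that prompted it, and that the code always means a move to the reduced scheme. The protocol supports neither assumption in every case. From a cycle 1 AE the earliest effective injection is two cycles later. A weight-loss reduction is already expressed by the normal table at the lower weight, so switching to Table 9 lowers the denominator a second time.

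At stake is the descriptive summary of whether extension injections were delivered as planned. Where the rule fails, children dosed as the protocol directs look over- or under-dosed in the table, and these are children with dose-relevant AE records.

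**Working it through.** The documents state no compliance figure to reproduce, so the check traces the rule for a child dosed as the protocol directs.

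**Inputs**
- Compliance = 100 × injected / planned (SAP 7.6).
- Concentration is fixed: 100 U / 4.0 mL = 25 U/mL (Protocol 8.1.1). A ratio of volumes therefore equals a ratio of units.
- The contents of the normal and reduced dosing tables are not shown. **Assumption:** the reduced scheme lies a fraction x below the normal scheme at the same weight, with x = 10%, 20%, 25% or 33% (one third) for illustration.

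**Formulas**
- Full dose given, reduced dose taken as the plan: 100 / (1 − x).
- Reduced dose given, full dose taken as the plan: 100 × (1 − x).

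| x | 100/(1 − x) | 100 × (1 − x) |
|---|---|---|
| 10% | 111.1% | 90.0% |
| 20% | 125.0% | 80.0% |
| 25% | 133.3% | 75.0% |
| 33% | 150.0% | 66.7% |

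**Case 1: cycle 1 AE coded *dose reduced*, stable weight, literal rule.** The protocol gives the full dose in cycle 2 and the reduced dose in cycle 3. The SAP plans the reduced dose in cycle 2 and, the next cycle having passed, the full dose in cycle 3. Apparent compliance is 111% to 150% in cycle 2 and 90% to 67% in cycle 3.

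**Case 2: the same child, with the Table 9 heading read as limiting the reduced plan to injections 3 and 4.** Cycle 2 returns to 100%. Cycle 3 still reads 90% to 67%, because no sentence links a cycle 1 AE to the cycle 3 plan.

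**Case 3: an AE record carries *dose reduced* because of weight loss.** The child receives the normal-table dose for the lower weight. The SAP compares it with Table 9 at that weight, giving 111% to 150%.

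**Case 4: AE in cycle 2 or 3, stable weight.** The next cycle is the cycle in which the reduction takes effect, and carry-forward covers cycle 4. Compliance is 100%, so the rule works here.

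**Effect on the extension mean.** In case 1, with cycle 4 at 100%, the per-subject mean is (111.1 + 90.0 + 100)/3 = 100.4% at x = 10% and (150.0 + 66.7 + 100)/3 = 105.6% at x = 33%. The two errors largely cancel, so the mean can look acceptable while two cycles are wrong. In case 2 nothing offsets the cycle 3 error: (100 + 90.0 + 100)/3 = 96.7% down to (100 + 66.7 + 100)/3 = 88.9%.

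**The case against.** The strongest reply has four parts.

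- **Cycle 2.** The reduced plan exists only in Table 9, whose heading confines it to the third or fourth injection, so cycle 2 cannot be mis-scored. This is a fair reading. It protects cycle 2 but leaves cycle 3 uncorrected.
- **Weight loss.** The action code sits on an AE record, so weight loss without an AE triggers nothing, and the SAP mentions the code only as an example. Both SAP and protocol also say that only one reduction applies when weight loss and an AE coincide. The first part stands and narrows the case to AE records that carry the code for weight loss, as Protocol 10.1.3 provides. The one-reduction sentence shows intent but does not say which denominator to use.
- **Detection of real errors.** A reader might infer that true dosing errors would be hidden. The documents do not support that. SAP 7.6 (Extent of exposure) tabulates units and U/kg per injection and lists children with a dose reduction, all protocol deviations are listed, and Protocol 8.2.6 has departures from the dosing scheme reported as AEs.
- **Size.** A reader might fill in the missing tables with six equal steps from 20 to 75 U (20, 31, 42, 53, 64, 75). If the dosing classes match the baseline weight classes in SAP 7.6, with lower bounds of 15, 19, 23 and 27 kg, the middle doses give 31/15 = 2.07, 42/19 = 2.21, 53/23 = 2.30 and 64/27 = 2.37 U/kg. SAP 7.7.5 puts planned exposure below 30 kg at no more than 2 U/kg, so those steps cannot be used to size the effect.

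**Conclusion.** The point holds, with a narrow scope. For a cycle 1 AE coded *dose reduced*, the stated rule scores a child dosed as the protocol directs below 100% in cycle 3 on either reading of Table 9, and above 100% in cycle 2 on the literal one. For an AE record coded *dose reduced* because of weight loss, it shows apparent over-dosing.

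A reader might infer that every child with an AE-driven reduction is mis-scored, or that the efficacy result is at risk. Neither follows. Case 4, which includes the SAP's own example, is handled correctly. Compliance is descriptive, only extension cycles are affected, and nothing in the text ties it to the per protocol set.

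The ranges of 111% to 150% and 90% to 67% rest wholly on the assumed x of 10% to 33%; the true values may lie outside them. The documents give no count of affected children. SAP Appendix 1, a separate file, was not available and might contain a finer rule. This is a minor point that is cheap to correct.

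**What to change.** Reconcile SAP 7.6, including the text under Table 9, with Protocol 8.2.2, 8.2.3 and 10.1.3. Replace the next-cycle wording with a derivation made for each injection: the planned volume is that of the dosing scheme the protocol assigns at that visit, using the weight measured there and the documented reason and effective injection of any reduction. The AE action code alone should not set the plan.

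The same edit should state the denominator in two situations that the rule leaves open:
- weight gain together with an AE that calls for a reduction, where the child stays at the previous level;
- the 12 to 15 kg group, which has no reduced level.

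No view is taken here on which dosing rule is right; the request is only that the denominator follow the reconciled one. The cost is a few SAP sentences and minor programming. Weight is already re-determined at each injection visit and children with dose reductions are already listed, but the team should confirm that the reason and effective injection can be read from the data.

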#### Table 9: Dosing scheme with dose reduction in the third or fourth injection

If in the third cycle the dose is reduced, then the fourth cycle dose will likewise be determined by reference to Table 9, using the subject's current body weight.

In the event of a subject's gaining weight such that he/she would progress from one dose level to a higher dose level according to Table 8, while at the same time requiring dose reduction because of a relevant adverse event, the subject will remain at the previous dose level.

In the event of a subject's losing weight and the occurrence of a relevant AE, only one dose reduction is allowed at the next injection session.

A frequency table for the method of administration of the injection per cycle will be displayed (ultrasound and other) for SES and FAS of MP and SES of OLEX.

A frequency table for the use of analgesics and/or sedatives during injection will be displayed (yes and no) for SES and FAS of MP and SES of OLEX.

# 7.7 Special Statistical/Analytical Issues

# 7.7.1 Discontinuations and Missing Data

Reasons for premature discontinuation by a subject will be summarized descriptively and listed. Where the discontinuation was due to an adverse event, this will be included in the listing of adverse events, and such events will be included as a category in the summary of adverse events.

The analysis of the primary and secondary efficacy variables will be performed using a MMRM as well as using an ANCOVA based on observed cases and an ANCOVA with missing values replaced by the baseline value or "no change" ('baseline observation carried forward approach'). By using all values of the dependent efficacy variable available in the timeframe underlying the MMRM, i.e. the main period, the MMRM reduces the influence of single missing values. The use of the ANCOVA model with missing values replaced by the baseline value is considered to be a conservative approach because if a comparable percentage of missing values is expected in both treatment groups (in the placebo group there may be more missing values due to lack of efficacy and in the verum group more due to adverse events) the replacement of missing values by the baseline value of the GICS – leads to a decrease in the difference of the observed treatment effects.

In general, values measured at the baseline injection visit (V2) will be used as study baseline value. If data is missing for this visit the last valid value before first injection will be used instead.

# 7.7.2 Interim Analyses

No interim analysis is planned for this study except from the analyses providing tables and listings for the DMC meetings.

# 7.7.3 Data Monitoring Committee

An independent DMC is assigned to monitor subjects' safety throughout the clinical course of the study. It consists of an odd number (e.g., three) of physicians who are suitably qualified and who have experience in analyzing pediatric clinical trial data, to allow majority decisions to be made. The primary purpose of the DMC is to safeguard subjects by monitoring AESIs, SAEs and AEs on a regular basis.

The DMC meets at regular intervals, either physically or remotely by secure teleconference during the main and extension period to review safety data. They decide upon and prioritize any safety issues and actions for the attention of the sponsor. The DMC is semi-blinded with respect to treatment group comparisons based on frequency tables. Subject data listings contain no treatment group information such that the DMC remains blinded with respect to individual subjects unless the treatment codes of individual subjects with AESIs, SAEs and AEs are unblinded for the DMC on request, by using the Interactive Web Response System (IWRS).

If considered necessary, the DMC makes recommendations regarding the timely management of subject withdrawals and/or measures for the study if there are relevant safety findings.

The DMC can make recommendations, if necessary, such as the following:

- Changes in study design (such as lowering the dose, additional telephone contacts etc.).
- Changes in timing of assessments.
- Implementation of additional safety measures.
- Unblinding of subjects if required for safety reasons.
- Prematurely discontinuing dosing in an age group.
- Prematurely discontinuing dosing in all age groups.
- Putting the study on hold.
- Stopping the study

For each DMC meeting, minutes are taken by the responsible DMC coordinator/administrator of the Contract research organization (CRO) and reviewed by the DMC members before finalization.

Details of responsibilities and procedures to be followed by the DMC are laid down in the DMC Charter.

A list of members of the committee and a copy of the committee's charter are provided separately and is reviewed by the Independent Ethics Committee (IEC)/ Institutional Review Board (IRB).

